### **Primary Endpoints and Data Analysis Plan**

Primary endpoints will include 1) changes in objective child physical activity, as measured via 7-day accelerometer at baseline and 1 year, including minutes/day MVPA in childcare center, minutes/day MVPA total; 2) classroom observation of child screen-time, as measured with EPAO observation method to quantify average minutes/day screen-time in childcare center; and 3) parent reports of child screen time to quantify minutes/day screen-time total. Age, sex, BMI z-score, and sociodemographic characteristics will be included as covariates. We will also assess the cross-sectional and longitudinal associations among sedentary behavior (by screen-time observation/self-report and by accelerometry), physical activity (by accelerometry), and fundamental motor skills.

A repeated measures ANCOVA model will be used to test for effects of policy implementation on each dependent continuous variable (minutes/day MVPA in childcare center, minutes/day screen-time in childcare center, minutes/day MVPA total, minutes/day screen-time total). Covariates will include age, sex, BMI z-score, and sociodemographic characteristics. Correlations and a repeated measures ANCOVA will be used to test for the relationships among sedentary behavior, physical activity, and change in fundamental motor skills.

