#### Inclusion Criteria:

- A child who is 3 or 4 years old
- Child spends at least 6 hours per day, 5 days per week at a participating childcare center
- Child will continue to attend the same childcare center for the next year

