Fundamental Motor Skill Assessments. The Test of Gross Motor Development - 3rd edition (TGMD-3) and the Movement Assessment Battery for Children - 2nd edition (MABC-2) will be administered with the cooperation and support of the childcare center staff in small group settings. Groups of approximately 3-4 students will complete the assessments together. The TGMD-2 uses direct observation to evaluate performance on 13 skills including running, horizontal jumping, hopping, skipping, sliding, galloping, and balls skills (two-hand striking, one-hand striking, catching, kicking, overhand throwing, underhand throwing and dribbling). The TGMD-2 involves a trained administrator demonstrating the proper execution of the skill, and the participant is allowed one practice trial then two formal trials that will be evaluated. The MABC-2 examines eight tasks that are categorized as manual dexterity, balance, aiming and catching. This is a field-based assessment that examines correct performances on a variety of skills that are not evaluated by the TGMD-3 and will provide a holistic picture of children's motor abilities. These assessments will be audio and video recorded.

Physical activity. Physical activity and time spent in moderate to vigorous physical activity will be measured by a triaxial accelerometer (Actigraph GT3X+, Actigraph of Ft. Walton Beach, FL). Children will be measured on 7 full days during the baseline and follow-up periods. The child will be outfitted with the accelerometer on an elasticized belt, on the right mid-axillary line. The Actigraph is one of the most common accelerometers used for scientific purposes, and the GT3X+ version provides extensive data on steps/day and time spent in various activity intensities. Parents will be encouraged to have their child wear the accelerometer 24 hours per day for at least 7 days (plus an initial familiarization day and the morning of the final day), including 2 weekend days. During wear weeks, study staff will check accelerometry wear during school hours to assess for compliance. Accelerometer use will be documented and parents of children who do not have accelerometers on wear check days will be contacted via call, text, flyer, email, etc. as a reminder. The minimal amount of accelerometer data that will be considered acceptable is 4 days with at least 10 hours of

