wear time per day, including at least one weekend day. Following the final day of data collection, the research team will verify the data for completeness using the most recent version of the ActiLife software (version 5.6 or higher; ActiGraph, Pensacola, FL) available at the time. The research team will ask the parents to have the children wear the accelerometer for additional days (to a maximum of 14 days) to ensure that minimal data requirements are met. Cut points will be assigned based on Van Cauwenberghe et al., with 0 to 372 counts per minute (CPM) classified as sedentary, 373 to 584 CPM as light, 585 to 880 CPM as moderate, and  $\geq 881$  CPM as vigorous. MVPA will be defined as total minutes  $\geq 585$  CPM.

**Screen time.** Screen time will be assessed using classroom observation at the childcare center (from the EPAO observation in Aim 1) and parent-report for screen-time outside of the childcare center. Parents will complete a survey adapted from Jago et al. to provide information about the child's screen-time (separately for TV, computer, games console and smartphone) on weekdays and weekend days. For each item the parent will be asked to report the time the child spent using it for (a) a normal weekday and (b) a normal weekend day, with response options: none; 1 to 30 minutes; 31 minutes to 1 hour; 1 to 2 hours; 2 to 3 hours; 3 to 4 hours; 4 hours or more. The assessment of TV viewing using parental report has been shown to correlate moderately ( $r=0.60$ ) with 10 days of TV diaries among young children.

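### Neither wear time nor time in care enters the two MVPA primary endpoints or their model, so a change in mean observed hours between baseline and 1 year would bias the estimated policy effect in either direction

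*Combined protocol and SAP*

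**What the plan says.** The Primary Endpoints and Data Analysis Plan section gives the two accelerometer endpoints as "including minutes/day MVPA in childcare center, minutes/day MVPA total". The Physical activity paragraph of Procedures says "MVPA will be defined as total minutes" at or above 585 counts per minute. On the analysis, "A repeated measures ANCOVA model will be used to test for effects of policy implementation on each dependent continuous variable". The adjustment set is stated twice, the second time as "Covariates will include age, sex, BMI z-score, and sociodemographic characteristics".

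Hours are addressed in three places:

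- **Eligibility.** "Child spends at least 6 hours per day, 5 days per week at a participating childcare center" (Inclusion Criteria), together with an expectation of staying at the same center for the next year.
- **Valid wear.** The rule in Procedures begins "The minimal amount of accelerometer data that will be considered acceptable is 4 days with at least 10 hours of"; the hours meant are those worn on each day, and one or more of the days must fall on a weekend. Parents are asked for round-the-clock wear, and wear can be extended to 14 days if data fall short.
- **Monitoring.** "During wear weeks, study staff will check accelerometry wear during school hours to assess for compliance". Use is documented and parents are reminded.

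The visit table (Train Schedule), the parent survey description and the accelerometer procedures list no arrival or departure times. They do not say how accelerometer time is divided between the center and elsewhere.

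**The concern.** A sum of minutes grows with the time over which it is accumulated. The two floors set minimums and do not make observed hours equal at the two waves. The 10 h wear floor applies to the whole day and not to hours in care. No sleep or non-wear rule is stated, so overnight wear could count toward it. In a 7-day period with two weekend days, 4 valid days may include only two weekdays, so one absence or early pick-up could weigh heavily in a child's in-center mean. The attendance floor applies at entry, and no re-check at 1 year is described.

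Aim 2 compares the same children before and after the regulations, and the documents describe no comparison group that would absorb a general shift in attendance or belt compliance. If mean hours rise, minutes/day can rise with no change in how active children are per hour. If mean hours fall, a real gain can be hidden. In-center MVPA is the accelerometer endpoint closest to the regulation, and as the plan is written the study could not show whether in-care hours had changed.

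**Working it through.** **Inputs from the documents.** Enrolment 266, dropout 25%, alpha 0.05 (Power Analysis). That section gives no effect size, SD, power or sidedness.

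**Assumptions.** Two-sided test; paired normal approximation; clustering within the 10 centers ignored; SD of within-child change 10 to 25 min/day; MVPA accruing at a constant 4 to 8 min per observed hour; mean shift in observed hours of 0.25 or 0.5 h.

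**Step 1, the plan's own figure.** 266 × 0.75 = 199.5, and 199 / 0.75 = 265.3, which rounds up to 266. The dropout step is consistent with 199 completers. The 199 itself cannot be derived from what is stated.

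**Step 2, detectable change.** With 199 pairs and 80% power: (1.960 + 0.842) / √199 = 2.802 / 14.107 = 0.199 SD.

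**Step 3, artefact from a shift in hours.** Artefact b = rate × mean change in observed hours.

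- 0.5 h at 4, 6 and 8 min/h: 2, 3 and 4 min/day.
- 0.5 h at 3.75 min/h (30 min in an 8 h day, also an assumption): 1.9 min/day.
- 0.25 h at 6 min/h: 1.5 min/day.

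**Step 4, rejection probability when the true policy effect is zero.** SE = SD / √199, and P = Φ(b/SE − 1.96) + Φ(−b/SE − 1.96). At 6 min/h:

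| SD of change (min/day) | Detectable change, 80% power (min/day) | P, 0.25 h shift | P, 0.5 h shift |
|---|---|---|---|
| 10 | 2.0 | 56% | 99% |
| 15 | 3.0 | 29% | 81% |
| 20 | 4.0 | 18% | 56% |
| 25 | 5.0 | 14% | 39% |

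Example: SD 15 gives SE = 15 / 14.107 = 1.063; 3.0 / 1.063 = 2.82; Φ(2.82 − 1.96) = Φ(0.86) ≈ 0.81. Over 4 to 8 min/h with a 0.5 h shift, P runs from 20% (4 min/h, SD 25) to nearly 100% (8 min/h, SD 10).

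**Step 5, after adjustment.** If MVPA is proportional to observed hours and those hours are correctly adjusted for, the artefact is 0 and P returns to 5%.

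**The case against.** Several points on the other side stand.

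- **Hours are not ignored.** A reader might infer that the plan takes no account of them. It has an attendance floor, a wear floor, documented wear checks, reminders and extra wear days. These limit poor data, although they do not equalise hours between waves.
- **The spread between children is the wrong contrast.** At 3.75 min/h, a child in care for 10 h scores 37.5 min and one in care for 6 h scores 22.5 min, and it is tempting to call that 15 min/day gap the bias. The analysis is of within-child change, so stable differences cancel. Only a change in mean hours biases the result, and a 15 min/day bias would need mean hours to rise from 6 to 10. Random variation in attendance adds noise only.
- **The direction is open.** A reader might infer that hours will lengthen and produce a false policy effect. The documents give no figure for any shift, in either direction.
- **A valid day may run from 10 to 24 h, but this overstates exposure.** Hours of sleep add almost no MVPA.
- **Silence is not proof.** It does not follow that in-center time must be cut by an assumed clock window. A manual of procedures is scheduled (Study Timeline), and the Aim 1 observation procedures are not in this document. A center schedule might be recorded there, though that would not give each child's own arrival and departure.
- **Minutes/day suits the regulation,** which sets a daily amount. If activity comes in scheduled blocks, extra hours may add little, and a per-hour rate could make a longer day look like a decline. This counts against replacing the endpoint with a rate. It does not count against adjusting for hours.

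Allowing for clustering would normally widen the SE, which raises the detectable change and lowers the rejection probabilities above.

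**Conclusion.** The concern holds in a conditional form. Wear and attendance have only floors, neither enters the MVPA endpoints or the stated covariates, and no visible procedure records arrival and departure. With no comparison group described, a change in mean observed hours between waves would pass into the estimated policy effect, upward or downward.

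The illustration shows that a modest shift would be enough to matter: the artefact from 0.5 h is about as large as the smallest change the study could detect with 80% power. It rests on an assumed shift, hourly rate and SD, on MVPA being proportional to hours, and on independent children. It does not show that such a shift will occur. The documents do not support reading this as a predicted false positive or as a bias of 15 min/day.

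**What to change.** In the Primary Endpoints and Data Analysis Plan section, keep minutes/day as the endpoint and add:

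1. **Total MVPA:** accelerometer-derived waking wear hours, sleep excluded, as a time-varying covariate. State the sleep and non-wear rules. This uses data already collected.
2. **In-center MVPA:** wear hours within the in-care window as a time-varying covariate, with days absent from care dropped.
3. **The window:** where centers keep sign-in and sign-out records, have on-site staff copy them for each wear day at both waves. Otherwise use the same pre-specified center-hours window at both waves, accepting that it is less exact for late arrival or early pick-up.
4. **Sensitivity analysis only:** MVPA per in-care hour.

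The model must take covariate values that differ between waves, for example as a mixed model for repeated measures.

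The cost is one extra covariate per MVPA model and minor data entry by staff who are already at each center for about 2 weeks per wave. The sign-in step depends on center records that the documents do not mention; item 1 does not.

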### **Number of Subjects and Subject Timeline**

We plan to enroll 266 children. Each child will participate in the study for approximately 1 year. Surveys, anthropometric measures, fundamental motor skill assessments, and screen-time observations will take approximately 2 days to complete, and the child will be given an accelerometer to wear at home for 7 days at both baseline and 1 year follow-up. Staff members will spend approximately 2 weeks at each childcare center at baseline and 1 year follow-up to complete study procedures with each child.

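### Primary endpoint 3 is labelled total screen time, but its only named source, parent report, is limited in the Procedures to time outside the childcare center

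*Combined protocol and SAP*

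**What the plan says.** Two sections describe the same measurement.

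- **Procedures, Screen time.** Measurement is divided by setting. In the center it is EPAO classroom observation, taken from Aim 1. Elsewhere it is "parent-report for screen-time outside of the childcare center". For each of four devices (TV, computer, games console, smartphone) the parent reports "the time the child spent using it for (a) a normal weekday and (b) a normal weekend day", choosing one of seven bands from none to an open category starting at 4 hours.
- **Primary Endpoints and Data Analysis Plan.** Endpoint 2 uses the EPAO observation "to quantify average minutes/day screen-time in childcare center". Endpoint 3 is "parent reports of child screen time to quantify minutes/day screen-time total". The repeated measures ANCOVA then tests for policy effects on four separate outcomes: "minutes/day MVPA in childcare center, minutes/day screen-time in childcare center, minutes/day MVPA total, minutes/day screen-time total".

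Neither section states that observed center minutes are added to parent-reported minutes. No rule is given for converting bands to minutes, summing over devices, or weighting weekdays against weekend days.

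**The concern.** A source limited to time outside the center cannot by itself yield a total. The regulation acts inside the center, so a total built this way would omit the part of the week in which the direct effect is expected. Two wrong conclusions could follow: that a policy which worked in the center did nothing to total screen time, or that screen use merely moved from center to home was an overall increase.

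The word also carries two meanings in one list. Both MVPA outcomes come from a single accelerometer ("Parents will be encouraged to have their child wear the accelerometer 24 hours per day for at least 7 days"), so total MVPA contains in-center MVPA. As sourced, total screen time does not contain in-center screen time, although the two pairs are presented in parallel.

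**Working it through.** The plan gives no expected value or change for total screen time, so there is no figure to reproduce. The check is on definitions, followed by arithmetic on direction and scale.

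**1. What each reading would produce**

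| Reading of total | Support in the text | Consequence |
|---|---|---|
| Parent report, outside center only | Scope stated in Procedures; sole source named in the analysis plan | Regulated setting omitted |
| EPAO minutes plus parent report | The sources are presented as complementary; no sum is stated | A true total, but only if parents exclude care hours; derivation rules missing |
| Parent report of the whole weekday | The item, as described, asks about a normal weekday with no exclusion of care hours | Label fits, but includes hours parents do not observe; adding EPAO would double count |

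These are three different variables. Only the first follows both sections as written.

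**2. Direction under the first reading**

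Let *d* be the minutes per care day removed in the center. Assume five care days a week (Inclusion Criteria) and a 5:2 weekday/weekend average, which the plan does not state.

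- In-center time falls by *d*, home unchanged: true total changes by −5*d*/7; the outside-only variable changes by 0.
- *d* moves from center to home: true total changes by 5(−*d* + *d*)/7 = 0; outside-only time rises by 5*d*/7.

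With *d* = 10 as a unit of arithmetic, not an expected effect, 5 × 10/7 = 7.1 min/day. That is the change in the underlying quantity, not what the survey would record.

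**3. What the banded survey would record**

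In minutes, the bands are 0, 1–30, 31–60, 60–120, 120–180, 180–240, and 240 or more. Assume midpoint scoring (0, 15.5, 45.5, 90, 150, 210) and 5:2 weighting. A 10-minute rise on one weekday item either stays within its band and records 0, or crosses one edge:

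- 0 to 15.5: 15.5 × 5/7 = 11.1 min/day
- 15.5 to 45.5: 30 × 5/7 = 21.4 min/day
- 45.5 to 90: 44.5 × 5/7 = 31.8 min/day
- 90 to 150, or 150 to 210: 60 × 5/7 = 42.9 min/day

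The open top band has no midpoint. A mean change across children therefore depends on a scoring rule and a response distribution that the document does not give.

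**4. Scale of the omitted part**

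Inputs are the background means in the Specific Aims: 1.3 h/day of screen time in centers and 4.1 h/day overall.

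- 1.3 × 60 = 78 min; 4.1 × 60 = 246 min
- 78/246 = 31.7% of a care day's screen time
- Over seven days: 78 × 5/7 = 55.7 min/day; 55.7/246 = 22.6%

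This assumes that both means apply to this cohort and can be set side by side. The Background section also quotes 1.5 to 7.0 h/day overall (90 to 420 min). Against that range, 78 min is anything from 78/420 = 19% to 78/90 = 87%, so the share is only a rough guide.

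**The case against.** The strongest reply is that the third reading may be the operative one. The item is described as asking about a normal weekday, with no stated exclusion of childcare hours. If the questionnaire reads that way, the label is right and nothing is omitted. This stands to the extent that omission cannot be asserted as fact: the questionnaire is not in the document. It does not remove the conflict, since the Procedures still limit parent report to outside time. It also replaces one problem with another, because parents would be estimating hours they do not see.

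A second reply is that the sum is plainly intended. It may be, but the analysis plan attributes the total to parent report alone, and a sum needs rules that are not written down.

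A third is that endpoint 2 measures the in-center effect directly. That is correct and limits the damage. A reader might infer that the study cannot detect an in-center policy effect on screen time; this problem with endpoint 3 does not support that.

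A reader might also infer a fixed bias, for example that 10 minutes moved to the home would be recorded as +7.1 min/day. The banded responses rule that out for a single item, and nothing in the document fixes the group mean.

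**Conclusion.** The point holds as a conflict between two sections over the source and scope of one primary outcome. That the sections disagree is certain from the text. That the resulting total omits the center holds on the reading that follows both sections as written, and it remains conditional on questionnaire wording that cannot be seen here.

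On that reading, an in-center reduction would not register and displacement to home would tend to look like an increase. Only the direction is supported. The 78 of 246 min is an illustration that assumes the background means apply and are comparable; it is neither an estimate of bias nor a predicted effect. The defect is confined to one of four dependent variables and to what may be concluded from it. It should be fixed, but it does not undermine endpoint 2 or the MVPA outcomes.

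**What to change.** First confirm how the weekday survey item is worded. Then choose one of two changes in the Primary Endpoints and Data Analysis Plan.

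1. **Relabel.** Call endpoint 3 parent-reported screen time outside the childcare center, and make no claim about total. This costs a wording change, provided the item excludes care hours.
2. **Define the sum.** Set total as EPAO-observed center minutes plus parent-reported outside-center minutes, and keep outside-center time as a separate variable so that displacement can be seen. State in advance:
   - how bands become minutes, including the open top band;
   - how the four devices are summed;
   - the weekday/weekend weighting, for example 5:2;
   - how a classroom observation is linked to each child.

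Option 2 is valid only if the weekday item explicitly asks about time outside childcare. If a survey wave was collected without that wording, say so as a limitation for that wave.

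Option 2 calls for no new type of data. The Train Schedule has the parent survey at baseline and follow-up, and the Number of Subjects and Subject Timeline section lists screen-time observations. That section shows only that observations are planned: its two days cover surveys, anthropometry and motor-skill tests as well. The feasibility of linkage depends on Aim 1 procedures that are not in this document. The price of option 2 is the added derivation choices and a likely need to allow for classroom or center clustering, since the observed component would probably be shared by children in the same room.

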### A Carrot and Stick Approach to Improve Community Policies

Over the past year, the Louisiana Department of Education (DOE) has been given authority of childcare center licensing in the state of Louisiana. A 2012 state legislative mandate seeks to create a unified early childhood system under the DOE. With this transition, all licensing requirements are being revised; early care and education programs are being organized under local childcare center networks; new standards are being implemented for all childcare center providers that accept public funds; and a quality rating system is being redeveloped. Specific to the proposed project, new licensing standards will affect children attending over 1,300 licensed childcare centers state-wide and include: 1) physical activity of at least 1 hour/day and 2) screen-time prohibited for children younger than 2 years and limited to 2 hours/day for children over 2 years. Childcare centers in East Baton Rouge Parish must begin implementing changes by 2016 to renew their annual license.

In addition to the mandated regulations, the DOE is also offering new training and programmatic opportunities to help childcare centers achieve the regulations. The DOE has engaged directly with childcare centers around the state by supporting the implementation of the Nutrition and Physical Activity Self-Assessment for Child Care (NAP SACC) intervention, which is funded by the state's Maternal and Child Health Title V Block Grant and 1305 funding. NAP SACC is a national evidence-based intervention to prevent and reduce childhood obesity. It is implemented in childcare centers and is designed to promote healthy weight development in preschool children by improving the nutritional quality of food served, amount and quality of physical activity, staff-child interactions, nutrition and physical activity policies and practices, and related environmental characteristics. Over 200 centers have participated in the program and have integrated practices that support healthy weight behaviors since NAP SACC began in Louisiana in 2010. The Louisiana DOE will train childcare center personnel in East Baton Rouge Parish on these new regulations in 2015-16, offering a natural opportunity to examine childcare centers before and after implementation of the new policy.

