### **Inclusion and Exclusion Criteria**

From the 10 selected childcare centers, 266 children and their parent(s) will be recruited to complete additional measures of physical activity and screen-time behaviors.

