### **Power Analysis**

A minimum of 266 children will be enrolled to ensure a well-powered study with significance level of  $\alpha = 0.05$  while allowing for a dropout rate of 25% between years 1 and 2. Estimation of change was based on data from Dowda et al., which observed a significant difference between MVPA in children in preschools rated low vs. high on physical activity environment.

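### The primary analysis ignores the 10 centres: the 0.05 level fails if one-year changes correlate within centre, and the claim of adequate power has no support for this design

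*Combined protocol and SAP*

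**What the plan says.** Under Primary Endpoints and Data Analysis Plan, four continuous variables are tested: MVPA in the centre, total MVPA, screen-time in the centre and total screen-time. For all four, "A repeated measures ANCOVA model will be used to test for effects of policy implementation on each dependent continuous variable". On adjustment: "Covariates will include age, sex, BMI z-score, and sociodemographic characteristics". Neither centre nor classroom is listed.

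The children are grouped: "From the 10 selected childcare centers, 266 children and their parent(s) will be recruited" (Inclusion and Exclusion Criteria). The exposure acts on the centre through its licence: "Childcare centers in East Baton Rouge Parish must begin implementing changes by 2016 to renew their annual license" (A Carrot and Stick Approach to Improve Community Policies).

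For in-centre screen-time, the Procedures section says: "Screen time will be assessed using classroom observation at the childcare center (from the EPAO observation in Aim 1". The visit schedule for the child lists no screen-time observation. The section on number of subjects, however, groups it with measures taken on the child: "Surveys, anthropometric measures, fundamental motor skill assessments, and screen-time observations will take approximately 2 days to complete".

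The Power Analysis section says: "A minimum of 266 children will be enrolled to ensure a well-powered study", at a significance level of 0.05 and "allowing for a dropout rate of 25% between years 1 and 2". It cites a study comparing MVPA between preschools with weaker and stronger activity environments. It gives no numerical power, effect size, SD, ICC or design effect.

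**The concern.** A repeated measures ANCOVA with child covariates treats the children's one-year changes as independent. Children in one centre share its staff, its response to the regulations and, because study staff visit each centre for about two weeks per round, the season of measurement. Any of these can make the changes of centre-mates alike. The standard error of the mean change is then too small and the test rejects too often.

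In-centre screen-time carries the greatest risk. If everyone in a room or centre is given one observed value, a handful of measurements is analysed as about 200.

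All four primary variables share the model, and the error runs towards false positives. The aims section plans to offer a positive result to the Gulf States region as a policy model. The sample size was not set with this structure in view, so the plan does not show what 10 centres can detect.

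**Working it through.** **Inputs from the documents.** 266 children, 10 centres, alpha 0.05 (two-sided assumed), 25% dropout. Completers: 0.75 × 266 = 199.5, taken as 200, or 20 per centre. **Assumed:** equal centre sizes, and an ICC of one-year change from 0 to 0.10, because none is given.

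**The plan's own figure.** 266 cannot be derived from the stated inputs. Working backwards, 199/0.75 = 265.3, rounded up to 266. A paired t-test on independent children needs 199 for a change of 0.20 SD at 80% power. That fits, but neither number is in the plan. A two-sample comparison at 0.40 SD and 80% power needs 198 in total, which gives 264, nearly as good a fit. Both treat children as independent.

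**Type I error of the child-level test.** Design effect DE = 1 + (20 − 1) × ICC. The approximate error is 2 × [1 − Φ(1.96/√DE)]. It was checked by simulating paired changes (40,000 runs, 10 centres of 20).

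**Detectable change.** Noncentral t with noncentrality δ/√(DE/200) on 10 − 1 = 9 df. 80% power needs a noncentrality of 3.15, so δ = 3.15 × √(DE/200), in SDs of child change.

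| ICC of change | DE | Error, formula | Error, simulated | Detectable change, 9 df |
|---|---|---|---|---|
| 0 | 1.00 | 0.050 | 0.049 | 0.22 SD |
| 0.01 | 1.19 | 0.072 | 0.073 | 0.24 SD |
| 0.02 | 1.38 | 0.095 | 0.094 | 0.26 SD |
| 0.05 | 1.95 | 0.16 | 0.16 | 0.31 SD |
| 0.10 | 2.90 | 0.25 | 0.25 | 0.38 SD |

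In the same simulation, a t-test on the 10 centre-mean changes rejected in 4.9% to 5.2% of runs. Treating children as independent (199 df) gives a detectable change of 0.20 SD.

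**Power of the 9-df test for an assumed change** (the documents state none):

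| Assumed change | ICC 0 | ICC 0.05 | ICC 0.10 |
|---|---|---|---|
| 0.20 SD | 71% | 44% | 32% |
| 0.30 SD | 96% | 77% | 60% |
| 0.40 SD | above 99% | 95% | 84% |

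**In-centre screen-time, only if observed values are shared.** With U distinct values copied equally to 200 children, the child-level t equals the unit-level t multiplied by √(199/(U − 1)). The error is the two-sided tail probability of a t on U − 1 df beyond 1.972/√(199/(U − 1)). The detectable change is in SDs of change between units, not between children.

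| Units U | Standard error understated by | Type I error | Detectable change, unit-level test |
|---|---|---|---|
| 10 (one per centre) | √(199/9) = 4.7 | 0.685 | 1.0 SD of centre change |
| 20 classrooms | √(199/19) = 3.2 | 0.550 | 0.66 SD of classroom change |
| 30 classrooms | √(199/29) = 2.6 | 0.458 | 0.53 SD of classroom change |

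The classroom counts are assumptions. Those rows also take classrooms in one centre as independent, so they are best cases.

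**The case against.** - **The inflation depends on an unknown.** At an ICC of change of 0 the level holds, and stable centre differences do cancel. Sociodemographic covariates might absorb part of the centre variation, which the unadjusted simulation does not represent. This stands as a limit on the size: the documents do not show which row of the table applies. It does not rescue the plan. If the ICC is near 0, a centre-level test costs little (0.22 against 0.20 SD); if it is not, the planned test is invalid.
- **The unit of analysis is never named.** True. Child level is inferred from the covariates and the count of children, and no other unit is offered. The inference is weakest for in-centre screen-time.
- **Shared screen-time values are not established.** Also true. The observation is borrowed from Aim 1, so its absence from the Aim 2 child schedule is suggestive only, and the section on number of subjects points the other way. Shared values remain the likely reading, but the 46% to 68% figures are conditional on it.
- **The power section cites a source.** It does, but what it takes from that source is a difference between preschools. The section gives no one-year change, SD or clustering allowance from it.
- **Inference could be confined to these 10 centres.** That would weaken the argument, but it does not fit an aim about licensed centres or the plan for regional dissemination.

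**Conclusion.** The concern holds. As written, the analysis understates the standard error whenever centres change unequally. With 20 completers per centre, an ICC of change of only 0.01 to 0.05 takes a nominal 5% test to roughly 7% to 16%, and 0.10 takes it to 25%. The ICC may be lower for total MVPA and total screen-time, which include hours outside the centre. For in-centre screen-time the error could reach 46% to 68% if observed values are shared, which the plan leaves open.

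The claim of good power is unsupported, not disproved: adequacy turns on an effect size, an SD and an ICC that the plan does not state. The figures rest on 200 completers, equal centre sizes and the assumed ICC range. The omission of centre is certain for the analysis and power sections; the exact inflation is not. The text needs correcting before analysis.

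**What to change.** 1. **MVPA and parent-reported screen-time.** Specify an analysis that respects centre, and name one as primary. One choice is a mixed model with random effects for child, centre and centre-by-time and small-sample degrees of freedom; it keeps the planned covariates. The other is a t-test on the 10 centre-mean changes (9 df); it is simpler, but it drops the covariates and weights centres equally. A centre main effect alone does not repair the test.
2. **In-centre screen-time.** State the level at which it is observed and analyse it there: classroom nested in centre, or one paired change per centre. Do not copy values to children. If children change classroom during the year, pair by centre. If total screen-time adds the observed in-centre value, say so and keep the centre-by-time term for that variable.
3. **Power.** Replace the unqualified claim with the detectable standardised change for about 200 completers in 10 centres over a stated ICC range.

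**Cost.** Changes to the analysis and power text only; no extra children or measurements. Confidence intervals widen, and the stated detectable change becomes less favourable. If in-centre screen-time has one value per centre, only a change of about 1.0 SD of centre change is detectable at 80% power, and the team may have to accept an imprecise estimate for that endpoint.
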